#### **Intervention Descriptions**

Apnea and Insomnia Relief (AIR). This treatment will be offered over six sessions. All six appointments will be conducted via telehealth and will last 60 minutes. The main components of the AIR protocol are (a) psychoeducation, (b) motivational interviewing, (c) PAP adherence strategies, and (d) cognitive behavioral therapy for insomnia. All of these components are based in established strategies from other behavioral interventions but have not been evaluated in a combined protocol. The table beneath this description provides for a session-by-session overview of the treatment.

**Psychoeducation.** Education about insomnia, sleep apnea, and PTSD is primarily provided in the first session, though it is interwoven into subsequent sessions based on each Veteran's needs. Sleep apnea education involves review of what sleep apnea is, how the severity of sleep apnea is measured (AHI), and understanding what his or her own AHI means (e.g., "I stop breathing 25 times each hour.") Veterans identify how sleep apnea affects functioning and quality of life, including nighttime symptoms, daytime symptoms, and impact of physical health. Veterans then learn about how PAP helps sleep apnea. Insomnia education involves definition of insomnia; in particular, early, middle, and late insomnia are defined, and the Veteran identifies which type(s) of insomnia he or she is experiencing. An emphasis is placed on how sleep apnea affects quality of sleep, while

insomnia may impact quantity of sleep. A brief review of PTSD symptoms, particularly sleep-related symptoms, is integrated into this component.

**Motivational interviewing.** Strategies to increase motivation for treatment will be employed throughout treatment as needed, but motivational interviewing is a particularly strong focus in the first session. The therapist will help the Veteran identify benefits to engaging treatment, both in the short-term and long-term. Veterans will be guided through specifying goals for treatment. They will also identify potential barriers to treatment as well as solutions to these barriers.

PAP adherence strategies. The Veteran will typically receive their PAP on the same day as their first treatment session. When the Veteran receives his or her PAP device, a certified sleep technician and/or respiratory therapist trained in sleep instructs the Veteran in the device's use and care. At the first AIR appointment, the therapist reviews with the Veteran how he or she can check his or her progress on the device itself. The therapist and Veteran work together to identify problems with and barriers to PAP use each week. This may include physical problems that require a return visit to the sleep technician (e.g., mask air leak from poor fit), and the therapist will prompt the Veteran to arrange an appointment. Another barrier that may be addressed is difficulty remembering to put the mask on before bed; the therapist will assist the Veteran in setting up reminders to facilitate PAP use. Should the Veteran experience anxiety, claustrophobia, or general discomfort (not stemming from a physical issue requiring further assessment by the sleep technician) related to PAP, which is not uncommon with PTSD or anxiety, the therapist will guide the Veteran though PAP desensitization. PAP desensitization will also be advised if the Veteran is removing the mask in the middle of the night.

**PAP desensitization.** PAP desensitization is a type of graded exposure that is used to acclimate Veterans to PAP. This is indicated in the case of Veterans who have increased difficulty falling asleep or back asleep with the mask on, experience anxiety or claustrophobia when using PAP, or who those who remove PAP (either consciously or unconsciously) while asleep. The Veteran will use their PAP (with mask and machine on) while awake. He or she will engage in another activity, such as listening to music or watching TV, rather than focusing on his or her breathing. By acclimating to the sensation of the PAP device while awake, the Veteran will become more comfortable using the device at night and will be more likely to tolerate it overnight. The therapist first explains the rationale for PAP desensitization to the Veteran. For Veterans with anxiety or claustrophobia caused by PAP, the therapist will introduce the Veterans to a rating scale to indicate their level of discomfort so that reductions in anxiety can be tracked. The therapist will also discuss coping strategies the Veteran can use while engaging in desensitization. The therapist will guide the Veteran through an in-session desensitization practice. Should the Veteran experience anxiety, the therapist will coach the Veteran through using coping skills and observing his or her anxiety levels decrease over the course of exposure. The therapist will then work with the Veteran to generate a plan for engaging in desensitization at home. It is recommended that the Veteran complete desensitization for 30 minutes daily.

**Cognitive Behavioral Therapy for Insomnia (CBT-I).** CBT-I is an established behavioral treatment for insomnia. Its main components are sleep restriction therapy and stimulus

control. Secondary components include sleep hygiene, cognitive strategies, and relaxation techniques.

Sleep restriction therapy. Typically, people with insomnia spend much more time in bed than they spend asleep. This means that they are sleeping inefficiently (i.e., their sleep is not consolidated.) The goal of sleep restriction therapy is to help the Veteran achieve consolidated sleep; rather than sleeping in several small chunks throughout the night, he or she instead falls asleep quickly and stays asleep. Using data from sleep diaries, the Veteran's average sleep ability is calculated (how much time the Veteran actually sleeps during the night). The Veteran's sleep opportunity (time in bed) is then matched to their sleep ability to limit their time in bed to how much sleep they are currently able to produce. (Note: a Veteran's sleep opportunity is not set to lower than five hours for safety reasons.) Over the course of treatment, the Veteran's bed time is moved 15 minutes earlier or later depending on how his or her sleep efficiency has been over the past week. Thus, the first step is consolidating the Veteran's sleep, and then we slowly expand the Veteran's sleep opportunity to help him or her learn to generate more sleep. A key part of sleep restriction therapy is having a consistent wake time to help the Veteran generate sleep drive over the course of the day. The therapist works with the Veteran to generate strategies to cut down on going to bed early, sleeping in late, and/or napping – all of which reduce the Veteran's sleep drive.

**Stimulus control.** Stimulus control is a behavioral strategy based in the concept of classical conditioning. As Veterans spend time in bed while awake, they build an association between the bed (i.e., BED = AWAKE.) This association can be perpetuated by engaging in activities in bed other than sleep or sex, such as watching television, using one's cell phone, or engaging in worry or rumination. Instead of BED = AWAKE, stimulus control promotes the association between BED = ASLEEP. This is accomplished by (a) using the bed for only sleep and sex, (b) moving other activities once done in bed to other locations, (c) only going to bed when feeling sleepy, (d) getting out of bed if unable to fall asleep or back sleep after 15-20 minutes, and (e) refraining from sleep in locations other than the bed. The therapist helps the Veteran implement these strategies.

Additional treatment components. Though the main components of CBT-I are sleep restriction therapy and stimulus control, later sessions cover additional material. The therapist helps the Veteran identify elements of sleep hygiene that may be improved, such as making the bedroom environment more comfortable or reducing caffeine intake in the afternoon and evenings. Another secondary element of CBT-I is a discussion of cognitions that may perpetuate insomnia. This includes attentional bias towards cues for sleepiness during the day and belief in several myths about sleep (e.g., 8 hours is everyone's ideal amount of sleep.) Though not a major focus of treatment, the therapist also introduces the Veteran to basic relaxation strategies that may be incorporated into the Veteran's bedtime ritual.

### Apnea and Insomnia Relief (AIR) session content

Session	Content
1	Psychoeducation about sleep apnea, insomnia, and PTSD; assessing/increasing motivation and identifying goals for treatment; learning to complete sleep diary
2	Continued motivational interviewing; Reviewing PAP experience; introducing PAP desensitization (in-session and at home) if needed; reviewing sleep diary; learning about sleep restriction
3	Reviewing PAP experience; continuing PAP desensitization; reviewing sleep diary; introducing stimulus control; continued motivational interviewing, if needed
4	Reviewing PAP experience; continuing PAP desensitization; reviewing sleep diary; sleep hygiene; continued motivational interviewing, if needed
5	Reviewing PAP experience; continuing PAP desensitization; reviewing sleep diary; cognitions about sleep; relaxation strategies; continued motivational interviewing, if needed
6	Reviewing PAP experience, continuing PAP desensitization; reviewing sleep diary; reviewing progress and relapse prevention

**Sleep Education Control (SE).** The control treatment will also be offered over 6 sessions via telehealth, to match time with the attention provided in the AIR condition. The protocol is an adaptation of the non-directive sleep education control condition in a study of CBT for insomnia among older adults at the Greater Los Angeles Healthcare System. Topics covered include the sleep cycle, sleep across the lifespan, sleep and the mind, evening activities and the sleep environment, and daytime activities and sleep. The table beneath this description provides for a session-by-session overview of the treatment.

# Sleep Education Control session content

Session	Content
1	Purpose of sleep, the sleep cycle/stages of sleep
2	Review of personal sleep history, sleep across the lifespan, aging and sleep
3	Consequences of poor sleep, stress and poor sleep, relaxation exercise
4	Healthy sleep environment: falling asleep (temperature, light, noise)
5	The body and sleep (physical exercise, diet)
6	Reviewing past sessions' content, most important tips to remember

Feasibility and Acceptability. Aim 2 of this study is to assess the acceptability and feasibility of AIR in Veterans with PTSD, insomnia, and OSA. We will assess feasibility and acceptability using a combination of Veteran self-report (questionnaire and interview) and behavioral metrics. The results of these inquiries will guide changes to treatment that must occur prior to the full-scale RCT that will be proposed in a VA Merit Review application.

Questionnaires. As described above, Veterans will complete the Feasibility and Acceptability self-report questionnaire at the post-treatment assessment (see Appendix 4). The items include questions specifically about the content of the intervention as well as use of telehealth. We will evaluate descriptive statistics for each item. On a group level, any item with less than moderate agreement (4.0 on 5.0 scale) will be identified as an element requiring further retooling in future work. Veterans will also complete the CSQ-8, a more global assessment of treatment satisfaction, to evaluate treatment satisfaction and assess differences between Veterans receiving AIR and Veterans receiving SE. \*This is for research purposes.

Interview. After completing the self-report questionnaires, the Veteran will meet with the Research Assistant to participate in an approximately 20-minute interview to obtain further information about his or her responses on the Feasibility and Acceptability Questionnaire. The RA will follow up about any items rated less than 4.0 on the Feasibility and Acceptability questionnaire. The RA will also probe for more information on the Veteran's experience in the telehealth sessions, including any aspects that were particularly positive or negative, and any problems encountered. \*This is for research purposes.

**Dropout.** An important aspect of feasibility and acceptability is behavioral: whether Veterans attend and complete treatment. We will examine whether there are differences in completion between AIR and SE. If there is higher dropout in the AIR condition, we will need to make thoughtful adjustments to the protocol prior to the full-scale RCT proposal based on Veterans' feedback about treatment. We will also examine when dropout does occur. If most dropout should occur immediately after randomization (as has been our experience in previous trials), we will be less concerned about the acceptability of treatment than if most dropout occurs later once treatment is initiated. \*This is for research purposes. Engagement in follow-up care. Veterans with new PAP setups in the Sleep Clinic are scheduled for a return visit with a sleep technician or nurse practitioner approximately three months following receipt of PAP. This visit is important to ensure optimal treatment and address any barriers to adherence and follow-up care in the case of non-adherence. If PAP is not going to be used, other treatments may be indicated (such as oral appliance or surgery), but if the Veteran does not attend this appointment, he or she is lost to follow-up and will go untreated. We will assess for differences between AIR and SE in attending this follow-up appointment. This analysis will only be applicable to Veterans with new PAP

Statistical Analysis Plan: Baseline characteristics of both groups (demographic, diagnostic, and pre-treatment levels of outcome measures) will be described using appropriate summary statistics. We will examine the distributions of outcome measures for outliers and evaluate the need to transform data. Identification of potential outliers will prompt review of data to evaluate for data entry errors; analyses including and excluding

setups that occurred during this participation in this study. \*This is for research purposes.

outliers will be conducted to evaluate influence on outcomes. Primary analyses will be unadjusted intent-to-treat analyses, with all subjects randomized to a treatment condition included. We will use linear mixed models, which are robust to data missing at random, to accommodate missing data due to dropout. Demographic and other baseline variables that show large group imbalances despite randomization will likewise be entered as covariates in a secondary sensitivity analysis, but will not be included in the primary analyses. Substantial differences in inferences supported by the primary and secondary analyses would indicate a potential problem of randomization failure, and would warrant caution in interpreting results of the primary analyses

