Clinical interview. Trained clinical interviewers will conduct the CAPS-5 interview to establish PTSD diagnosis and SCID-5 interview to establish insomnia diagnosis. This will take place over phone or video. The SCID-5 will also be used to rule out diagnostic exclusion criteria and establish comorbid mental health conditions for data analytic purposes. A brief medication interview will be conducted to obtain information about recent and current medication use. Interviews will be audio-recorded and reviewed by the Stress and Health Research Program's clinical assessment supervisor \*This is solely for research purposes.

Baseline prospective sleep data. Once eligibility is established, the Veteran will be shown how to complete a sleep diary. He or she will then record one week of baseline sleep data. Research staff will email the Veteran a link to enter sleep diary data via Qualtrics. The Veteran's PAP setup appointment (if needed) and treatment schedule will be planned. \*This is for research purposes; however, please note that completing a sleep diary is also part of routine care.

**Actigraphy.** The actigraph is a device worn on the risk to measure time asleep vs. awake. A subset of participants will be asked to wear the actigraph. The information will be used solely for research purposes. It is not part of the treatment.

**Baseline appointment**. The Veteran will complete pre-treatment measures. He or she will be randomized to either AIR or SE. \* Many of the pre-treatment measures are completed as part of routine care, but some are added for research purposes.

**Randomization procedure.** A block-randomization procedure will be used to assign participants to AIR or SE in a 1:1 ratio. Block sizes will be a random permutation of 4 and 6. Statistical consultant [REDACTED] will produce the computer-generated list. Each therapist will have his or her own randomization list. The randomization to treatment is for research purposes.

**Weekly assessment.** At the start of each treatment appointment, the Veteran will complete two self-report questionnaires assessing sleep (ISI and ESS). The Veteran's PAP adherence data and actigraphy data will also be downloaded or requested verbally. A copy of the Veteran's sleep diary will be obtained. At his or her final treatment appointment, the Veteran will be asked to complete a sleep diary to submit at the Post-Treatment

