Analyses for PAP adherence: PAP adherence will be measured via device data capture. The primary metric used to measure this will be average hours of PAP use in the past 7 days. This will be measured starting at session 1 and will continue through post-treatment, and again for 1 week at follow-up. A linear mixed model as described above for the ISI will be estimated for PAP adherence. The hypothesis will be tested by the significance of the group difference in marginal means at post-treatment derived from the full model. The difference in marginal means at post-treatment will be divided by the pre-treatment standard deviation to calculate the standardized effect size. Durability of effects at 3 months will be tested by comparing model-adjusted marginal effects for the two groups at follow-up. Effect size of treatment at 3 months will be calculated from the marginal effect of group at follow-up divided by the standard deviation of week 1 adherence scores. Hypothesis 2a: Veterans receiving the behavioral sleep treatment will report at least moderate agreement with items on the Feasibility and Acceptability Questionnaire. Analyses: Descriptive statistics will be calculated for each item of the Feasibility and Acceptability questionnaire, provided in the Appendix. The mean response to each item will be the primary metric for evaluation of this hypothesis. A mean in the range of 4.0 to

**Hypothesis 2b:** There will be lower dropout in the AIR condition compared with the SE condition.

**Analyses:** We will conduct a chi-square analysis to compare dropout in the two conditions (completed all six sessions vs. not).

**Hypothesis 2c:** There will be greater engagement in apnea care in the AIR condition compared with the SE condition.

**Analyses:** We will conduct a chi-square analysis to compare how many Veterans attend their first PAP follow-up appointment with a sleep technician or sleep NP in the two conditions.

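### Hypothesis 2c leaves out Veterans who needed a new PAP setup but never had one, so its attendance comparison is selected after randomization and may be biased in either direction

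*Combined protocol and SAP*

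**What the plan says.** The Engagement in follow-up care paragraph (under Feasibility and Acceptability) sets the analysis population in one sentence, which the text extraction has split: "This analysis will only be applicable to Veterans with new PAP" and then "setups that occurred during this participation in this study". The outcome is a routine visit. Veterans with new setups "are scheduled for a return visit with a sleep technician or nurse practitioner approximately three months following receipt of PAP".

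The Hypothesis 2c entry in the analysis plan gives the test: "We will conduct a chi-square analysis to compare how many Veterans attend their first PAP follow-up appointment". It states no denominator, and no rule for a Veteran who needed a setup and never had one. The intent-to-treat statement in the Statistical Analysis Plan covers primary analyses; Hypothesis 2c belongs to Aim 2, so that statement does not settle the matter.

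Three places fix the order of events:

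- Baseline prospective sleep data, once eligibility is established: "The Veteran's PAP setup appointment (if needed) and treatment schedule will be planned".
- Baseline appointment, described after that baseline week: "He or she will be randomized to either AIR or SE".
- PAP adherence strategies: "The Veteran will typically receive their PAP on the same day as their first treatment session".

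**The concern.** Need for a setup is a baseline characteristic. Completing it is normally a post-randomization event. The plan conditions on the second, so the groups compared are no longer the randomized groups.

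The Veterans removed also matter for the hypothesis. Hypothesis 2c is about engagement with apnea care, and the protocol treats a missed return visit as serious because the Veteran then goes without treatment. A Veteran who never collects the device is equally untreated, yet is left out rather than counted as a failure. This need not be rare. The Dropout paragraph says that in the team's previous trials most dropout came straight after randomization, when setups would still be pending. Recruitment also admits Veterans not yet connected to sleep care or no longer engaged in it.

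The arm could affect completion through early dropout, through setups that fall after session 1, or through AIR's motivational work, which is concentrated in session 1. The SE session list has no PAP content. Aim 2 results are meant to guide changes before a full-scale trial, so a distorted comparison has a practical cost.

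**Working it through.** The documents give no setup rate, attendance rate or sample-size basis for Hypothesis 2c, so there is no stated figure to reproduce. Every rate below is an assumption; only the 40 per arm comes from the protocol (Aim 1).

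**Set-up.** Among Veterans who need a new setup, let
- s = share set up under either arm,
- m = further share set up only under AIR,
- a = attendance under SE among the share s,
- e = true AIR gain in attendance among the share s,
- q = attendance among the added share m.

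Plan's denominator (set up only): SE = a; AIR = [s(a + e) + mq] / (s + m).
All who needed a setup: SE = sa; AIR = s(a + e) + mq.

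**Setup 80% (SE) v 90% (AIR): s = 0.80, m = 0.10, a = 0.70, q = 0.30.**

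| True gain e | AIR, set up only | v SE 70% | AIR, all in need | v SE 56% |
|---|---|---|---|---|
| 0 | (0.56 + 0.03)/0.90 = 65.6% | −4.4 points | 59% | +3 points |
| 5 points | (0.60 + 0.03)/0.90 = 70.0% | 0.0 | 63% | +7 points |
| 10 points | (0.64 + 0.03)/0.90 = 74.4% | +4.4 points | 67% | +11 points |

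The plan's comparison falls short of the true gain in each row. It changes sign only in the first; at 5 points it shows a tie.

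**Equal completion (m = 0, s = 0.80, e = 0.05).** Set up only: 75% v 70%, +5 points. All in need: 60% v 56%, +4 points. There is no selection problem.

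**Opposite direction.** Swap the arms (setup 90% SE, 80% AIR, e = 0, other values unchanged). Set up only: AIR 70% v SE 65.6%, +4.4 points. All in need: AIR 56% v SE 59%, −3 points. The bias now favours AIR.

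**When the sign changes.** AIR falls below SE among those set up when m/s > e/(a − q). With a = 0.70 and q = 0.30 this is m > s × e/0.40.
- s = 0.80, e = 0.05: m must exceed 0.10, i.e. more than 4 of 40.
- s = 0.80, e = 0.10: m must exceed 0.20, which is the whole remainder, so it cannot happen.
- s = 0.70: m must exceed 0.0875 (e = 0.05) or 0.175 (e = 0.10).
- s = 0.90, e = 0.05: m must exceed 0.113 when only 0.10 is available, so it cannot happen. With q = 0.10 the threshold is 0.90 × 0.05/0.60 = 0.075, so it can.

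**In counts (assumed, all 40 per arm needing a setup).** AIR: 36 set up, 24 attend. SE: 28 set up, 20 attend. Set up only: 24/36 = 66.7% v 20/28 = 71.4%, −4.8 points, p = 0.68. All randomized: 24/40 = 60% v 20/40 = 50%, +10 points, p = 0.37 (chi-square without continuity correction).

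**The case against.** The restriction has an ordinary purpose. Recruitment includes Veterans already on PAP but not adherent, and the sentence separates them from new users, who are the ones given a three-month return visit. That visit is timed from receipt of the device, so a Veteran without one has no such visit to miss. Widening the denominator changes what is estimated, because it joins device uptake to visit attendance. This stands in part, and is why the set-up-only comparison should be kept beside the main one.

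The route from AIR to setup is also narrow. The appointment is planned before randomization and the device typically arrives on the day of session 1, so little AIR content has been delivered by then. Session 2 already reviews PAP experience, and AIR's PAP strategies mostly concern a device in hand. Nothing says that early dropout differs by arm. If participation is taken to start at consent, some setups could precede randomization and be unaffected. All this stands, and limits the likely size.

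A reader might infer that the plan's comparison will make AIR look worse when it is better. The documents do not support that. They give no rates, and reversal needs a sizeable arm difference in completed setups together with little true effect on attendance or poor attendance among the added Veterans. Scenarios that set the AIR effect to zero produce a reversal by construction whenever the added Veterans attend less often than the rest.

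Finally, the plan monitors other PAP-related appointments, looks at when dropout occurs, and compares session completion in Hypothesis 2b. These are useful, but none puts the missing Veterans back into the Hypothesis 2c denominator. Nor does low power excuse the choice: in the count example neither p-value is near significance, but a pilot of this size will be read mainly for its estimates.

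**Conclusion.** The point holds as possible post-randomization selection. Followed as written, the plan removes Veterans who needed PAP and never received it from a test of engagement, and gives no comparison based on need at baseline. If setup completion differs by arm, the result may be biased in either direction; if it does not differ, the problem largely disappears.

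The size cannot be stated from the documents. At assumed setup of 80% v 90%, base attendance of 70% and 30% among the added Veterans, the plan's comparison shows 70.0% v 70% for a true 5-point gain and 74.4% v 70% for a 10-point gain. So there is no reversal in that setting once AIR raises attendance by 5 points or more. Sign reversal is an extreme case and should not be presented as the expected result.

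This is one Aim 2 measure in a pilot, not the primary outcome. It should be corrected because the correction is cheap and the results feed the design of the next trial.

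**What to change.** 1. Record before randomization, as a yes/no field, whether the Veteran needs a new PAP setup.
2. Use as the main Hypothesis 2c denominator all randomized Veterans with that need, by assigned arm. Count no setup, or no attendance at the first follow-up visit, as not engaged. Veterans who already have PAP remain outside the analysis, as the plan intends.
3. Report setup completion by arm beside it.
4. Keep the comparison among Veterans who were set up as supportive, and state in the Hypothesis 2c entry which denominator is the main one.

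The cost is a change of wording and one baseline field. Follow-up attendance is already checked in charts. The protocol does not say that need for a setup is stored as an analysis variable, so for anyone already enrolled it would have to be taken from scheduling records made before randomization, where these exist. The attendance rates will be lower, and the main measure will combine device uptake with return-visit attendance, which is why both components should be shown.
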